3.1.3 Product Description

The Product is The MetaNeb® System, a therapeutic device that provides airway clearance and lung expansion therapy. The MetaNeb® System is a marketed product, indicated for mobilization of secretions, lung expansion therapy and the treatment and prevention of pulmonary atelectasis. The device also has the ability to provide supplemental oxygen when used with compressed oxygen. The system has three therapy modes:

- CHFO (Continuous High Frequency Oscillation) – delivers aerosol therapy while providing oscillating pressure pulses to the airway
- CPEP (Continuous Positive Expiratory Pressure) – delivers aerosol therapy while providing continuous positive pressure to help hold open and expand the airways
- Aerosol – for delivery of aerosol only. In this mode, CHFO and CPEP are not available

3.1.4 Treatment Protocol:

All enrolled patients will receive therapy for airway clearance and lung expansion procedures using The MetaNeb® System. Other airway clearance and/or lung expansion therapies will not be delivered during the study period. The treatment regimen for other respiratory care modalities will be that which is prescribed by the patient's health care team in the routine standard care of each patient (e.g. oxygen, aerosolized medications, etc.).

Exceptions to the above treatment protocol required for patient care as determined by the treating physician will be collected.

3.2 Study Population

The study population consists of adult post-surgical (thoracic, cardiac or abdominal surgery) non-mechanically ventilated patients with evidence of significant atelectasis on chest x-ray, with an increasing need for respiratory support.

Hill-Rom®	Evaluation of The MetaNeb® System to reduce atelectasis as assessed by chest x-ray			Page 14 of 29
	CBI	06 March 2017	Rev C	CR-RR2016- 001

3.2.1 Inclusion Criteria:

Patients who meet all of the following criteria will be included in the study:

- Age \geq 18 years
- Significant atelectasis by chest x-ray
- Patient meets indications for therapy as defined by Recruitment and Airway Clearance Protocol (HOAG2013-0000002335/Version 4/Effective Date: 9/15/14)
- Signed informed consent

3.2.2 Exclusion Criteria:

Patients who meet any of the following criteria will be excluded from the study:

- Cause of atelectasis suspected to be infectious or solid mass
- Requirement for mechanical ventilation
- Requirement for chronic supplemental oxygen
- Hemodynamically unstable, as defined by need for vasopressor therapy
- Anticipated need for mechanical ventilation, or other poor clinical outcome, unrelated to atelectasis or secretion retention
- Contraindication to MetaNeb® therapy (untreated tension pneumothorax)
- Inability to perform MetaNeb® therapy using a mouthpiece
- Anticipated hospital discharge within 24 hours

3.3 Evaluation Criteria/Effectiveness

The therapy regimen (treatment with The MetaNeb® System) will be evaluated to determine if there is an improvement in chest x-ray scores after initiation of the therapy. The study will also evaluate if there is a corresponding improvement in the clinical respiratory status of the patients demonstrated by a decrease in the O₂ requirement and/or an improvement in oxygen saturation. Endpoints are described below:

Primary Endpoint:

Chest x-ray score improvement at Day 2 (approximately 48) hours after initiation of therapy with The MetaNeb® System.

Chest x-rays will be scored using the Kelly scoring system (Appendix 1) to assess the presence of atelectasis on Day 2, after initiation of therapy with The MetaNeb®

Hill-Rom®	Evaluation of The MetaNeb® System to reduce atelectasis as assessed by chest x-ray			Page 15 of 29
	CBI	06 March 2017	Rev C	CR-RR2016- 001

System. Scores for chest x-rays at Day 2 will be compared to the scores for chest x-rays taken at baseline. The Kelly score for each of the chest x-rays will be assessed by blinded reader.

The baseline chest x-ray for each subject is the qualifying x-ray that determined the presence of significant atelectasis.

Secondary Endpoint(s):

- Chest x-ray score improvement at Day 1 (approximately 24 hours) and at Day 4 (approximately 96 hours or at discharge, if discharge occurs before Day 4) after initiation of therapy with The MetaNeb® System.

Scored using the Kelly score, as described above, to assess the presence of atelectasis.

- Chest x-ray improvement using a comparative scale after a minimum of forty-eight (48) hours of therapy with The MetaNeb® System.

Chest x-ray improvement assessed using a comparative scale for baseline, Day 1, Day 2 and Day 4/discharge. Four chest x-rays for each enrolled subject (baseline, Day 1, Day 2 and Day 4/discharge), with date and time masked, will be sent to the radiologist for comparison. The radiologist will rank the four x-rays 1, 2, 3 or 4 (1 = least atelectasis, 4 = most atelectasis).

- Oxygenation index ($\text{SpO}_2/\text{FiO}_2$ ratio) at Day 1, Day 2 and Day 4/discharge compared to baseline
- Patient reported level of dyspnea (assessed by Modified Borg Dyspnea Scale – Appendix 2)
- Change in patient respiratory status (Respiratory Status Evaluation – Appendix 3)

Physician observation and evaluation of patient respiratory status at time of enrollment (baseline) and on Day 2

Safety:

- Device-related adverse effects (adverse device effects) will be collected and evaluated.

3.4 Study Observations Table

The study observations and documentation timeline is outlined in Table 1.

Hill-Rom®	Evaluation of The MetaNeb® System to reduce atelectasis as assessed by chest x-ray		
	CBI	06 March 2017	Rev C

Table 1. Study Observations

Day	Day 0 (Treatment Initiation)	Day 1 (Post Treatment Initiation)	Day 2 (Post Treatment Initiation)	Day 4 / Discharge (or Early Termination)
Selection Criteria / Enrollment	X			
Informed Consent	X			
Demographic Data	X			
Medical History	X			
Chest X-ray Score (Kelly)	X (Baseline)	X	X	X
Chest X-ray Ranking (Comparative)				X
O2 Requirement Collected at time of Baseline and Day 4 / Discharge Chest X-rays.				
Collected at beginning of each shift for Day 1 and Day 2	X	X	X	X
SpO ₂ Collected at time of Baseline and Day 4 / Discharge Chest X-rays.				
Collected at beginning of each shift for Day 1 and Day 2	X	X	X	X
Borg Dyspnea Scale	X	X	X	
Respiratory Status Evaluation	X		X	
MetaNeb Treatments	X	X	X	X
Study Exit Form				X

3.4.1 Study Observations Table Detailed Description

Documentation of observations will be completed by study staff at the time of occurrence, from review of the patient's medical records and from scores and rankings for chest x-rays completed by radiologist review. A detailed description of documentation requirements for each parameter is below.

Demographic Data: The following data will be recorded from the patient medical record: Age, Height, Weight, Race and Ethnicity, Gender.

Medical History: Admitting diagnosis, pulmonary history will be recorded from the patient medical record including: Asthma, CF, Bronchiectasis, COPD, Neuromuscular Disease, Obstructive Sleep Apnea or Other Pulmonary Condition(s).

Hill-Rom®	Evaluation of The MetaNeb® System to reduce atelectasis as assessed by chest x-ray		
	CBI	06 March 2017	Rev C

Chest X-ray Score (Kelly): Chest x-ray files will be collected beginning with the enrollment chest x-ray (Day 0) and for Day 1, Day 2 and Day 4 or at time of discharge from the hospital (if earlier). All chest x-rays will be logged by subject number, date and time, and event (i.e. Day 0, Day 1, Day 2, Day 4/discharge) and assigned a number from a random number list. All chest x-rays, identified only by the assigned number, will be placed in a file and then reviewed and scored by the radiologist(s). Radiologist(s) will be blinded to subject and event.

Chest X-ray Ranking (Comparative): Chest x-ray files will be collected for each subject beginning with the enrollment chest x-ray (Day 0) and for Day 1, Day 2, and Day 4 or at time of discharge from the hospital (if earlier). The random number assigned to each chest x-ray (Day 0, Day 1, Day 2, Day 4) will be used to identify the time and date. The group of chest x-rays for each subject, identified only by the assigned number, will be placed in a file and then reviewed, compared and ranked by the radiologist(s). Radiologist(s) will be blinded to subject and event.

O₂ Requirement: The oxygen support status for each subject will be recorded for the time of the baseline and Day 4/discharge chest x-rays. The oxygen support status will also be recorded for the beginning of each shift for Day 1 and Day 2.

SpO₂: The oxygen saturation (based on pulse oximetry readings) for each subject will be recorded for the time of the baseline and Day 4/discharge chest x-rays. The oxygen saturation will also be recorded for the beginning of each shift for Day 1 and Day 2.

SpO₂/FiO₂ Ratio: The SpO₂/FiO₂ ratio (based on pulse oximetry readings and the O₂ requirement) for each subject will be calculated for the time of each chest x-ray. The SpO₂/FiO₂ ratio will also be calculated for the beginning of each shift for Day 0 – Day 2, or until the time of discharge from the hospital (if earlier).

Assessment of Dyspnea (Modified Borg Dyspnea Scale): An evaluation of each subject's dyspnea level will be assessed using patient response and a Modified Borg Dyspnea Scale. Evaluation will be completed by respiratory staff at the time of enrollment into the study (Day 0), and on a daily basis for Day 1 and Day 2, or at the time of discharge from the hospital (if earlier).

Respiratory Status Evaluation: An evaluation of each subject's respiratory status will be completed by the physician investigator at the time of enrollment into the study (Day 0) and on Day 2, or at the time of discharge from the hospital (if earlier).

MetaNeb® Treatments: All MetaNeb® treatments will be documented for each day beginning with enrollment (Day 0), Day 1 and Day 2, and through Day 4 or until the time of discharge from the hospital (if earlier).

Hill-Rom®	Evaluation of The MetaNeb® System to reduce atelectasis as assessed by chest x-ray		Page 18 of 29
	CBI	06 March 2017	Rev C

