FiO ₂	Fraction of Inspired Oxygen
FDA	Food and Drug Administration
GCP	Good Clinical Practice
HIPAA	Health Insurance Portability and Accountability Act
ICU	Intensive Care Unit
IPV	Intrapulmonary Percussive Ventilation
IRB	Institutional Review Board
LE	Lung Expansion
LPM	Liters Per Minute
MV	Mechanical Ventilation
O ₂	Oxygen
PPC	Postoperative Pulmonary Complication
SpO ₂	Oxygen Saturation
SOP	Standard Operating Procedure

Hill-Rom®	Evaluation of The MetaNeb® System to reduce atelectasis as assessed by chest x-ray		
	CBI	06 March 2017	Rev C CR-RR2016- 001

Protocol Synopsis

Product Name:	The MetaNeb® System
Protocol Number:	CR-RR2016-001
Protocol Title:	Evaluation of The MetaNeb® System to reduce atelectasis as assessed by chest x-ray
Objective(s):	To evaluate the impact of use of The MetaNeb® System in clearance of atelectasis, as demonstrated by improvement in chest x-rays
Endpoints:	
Efficacy:
 
Primary Endpoint:
 
 • Chest x-ray assessed by Kelly Atelectasis Score [1] (Appendix 1) – Day 2 (approximately 48 hours) compared to baseline 
Secondary Endpoint(s):
 
 • Chest x-ray assessed by Kelly Atelectasis Score at Day 1 (approximately 24 hours) and at Day 4 (approximately 96 hours, or at discharge if discharge occurs before Day 4), compared to baseline • Chest x-ray improvement using a comparative scale (comparing baseline, Day 1, Day 2 and Day 4/discharge) • Oxygenation index (SpO₂/FiO₂ ratio) • Patient reported level of dyspnea - assessed by Modified Borg Dyspnea Scale (Appendix 2) • Change in patient respiratory status - subjective physician assessment –Respiratory Status Evaluation (Appendix 3) 
Safety:
 
 • Device-related adverse effects (adverse device effects) will be collected and evaluated.
Study Design:	The study will be a non-randomized open label study, with all subjects receiving treatment with The MetaNeb® System
Study Conduct:	The study will be conducted at one (1) site in the US.

Hill-Rom®	Evaluation of The MetaNeb® System to reduce atelectasis as assessed by chest x-ray	Page 7 of 29		
	CBI	06 March 2017	Rev C	CR-RR2016- 001

Treatment of Subjects:	Subjects who qualify for enrollment in the study will receive therapy with The MetaNeb® System following the labeled instructions for the device. Details of the treatment including duration and frequency will be defined in treatment procedures.

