3	Moderate	Exercise Training Zone
4	Somewhat severe	
5	Severe	
6		
7	Very severe	
8		
9	Very, very severe (almost maximal)	
10	Maximal	

Patient Instructions for Borg Dyspnoea Scale

"This is a scale that asks you to rate the difficulty of your breathing. It starts at number 0 where your breathing is causing you no difficulty at all and progresses through to number 10 where your breathing difficulty is maximal. How much difficulty is your breathing causing you right now?"

Hill-Rom®	Evaluation of The MetaNeb® System to reduce atelectasis as assessed by chest x-ray		
	CBI	06 March 2017	Rev C

Appendix 3

Respiratory Status Evaluation

MetaNeb® Study: Respiratory Status Evaluation			

Evaluate Patient's Pre-MetaNeb® therapy status based on the parameters listed below. Using these judgments as baseline reference points, score patient's respiratory and general health status following day two of MetaNeb® therapy.
 
 Worse (1)  Unchanged (2)  Improved (3)
			
Pre-treatment evaluation notes	Day 2 (48 Hour) Score	Comments	
1) Lung assessment: Percussion 
 • Resonance over hyperinflated areas • Dullness over consolidated areas • Location and excursion of diaphragm 	 Worse (1)  Unchanged (2)  Improved (3)		
2) Lung Assessment: Auscultation 
 • Sounds of normal air entry • Adventitious breath sounds (e.g. rhonchi, rales, pleural rub, stridor, decreased breath sounds) • Quality of breath sounds (e.g. bronchial, bronchovesicular, vesicular) • Inspiration/expiration ratio • Degree of air entry throughout chest (equal/unequal) 	 Worse (1)  Unchanged (2)  Improved (3)		
3) Cough Assessment 
 • Quality (effectiveness) • Severity • Frequency 	 Worse (1)  Unchanged (2)  Improved (3)		
4) Secretion Assessment 
 • Quantity • Consistency • Ease of clearance • Abnormal color/purulence 	 Worse (1)  Unchanged (2)  Improved (3)		

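### The Day 2 Respiratory Status Evaluation is a subjective rating by an unblinded investigator, and nothing requires it to be scored before the Day 2 film is seen or records the order

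*Combined protocol and SAP*

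**What the plan says.** The Protocol Synopsis lists among the secondary endpoints "Change in patient respiratory status - subjective physician assessment", using the form in Appendix 3. Section 3.4.1 states that the evaluation "will be completed by the physician investigator at the time of enrollment into the study (Day 0) and on Day 2", or at discharge if that is earlier.

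Appendix 3 has the investigator note the pre-treatment status and then, "Using these judgments as baseline reference points", "score patient's respiratory and general health status following day two of MetaNeb® therapy". Seven bedside domains are each scored Worse, Unchanged or Improved. The chest film is not one of them.

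The primary endpoint is a Day 2 film. Section 3.3 says "Scores for chest x-rays at Day 2 will be compared to the scores for chest x-rays taken at baseline". For the readers of those films, Section 3.4.1 says "Radiologist(s) will be blinded to subject and event". No masking is described for the investigator who scores the evaluation, and Section 3.1.1 describes the study as open label with every subject treated.

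Section 3.5.2 lists the evaluation as a secondary endpoint and does not relate it to the Kelly score.

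**The concern.** Two Day 2 assessments are made of the same chest, and only one is protected from outside knowledge. The bedside rating is a judgement of change against the investigator's own notes. An investigator who has just seen a clearer film, or read a report saying so, may hear and percuss a better chest.

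The content of the two instruments makes this route specific. The percussion item in Appendix 3 covers dullness over consolidation and the position of the diaphragm. The Kelly score in Appendix 1 grades extent along the hemidiaphragm, lobar consolidation and lobar collapse. The film therefore speaks directly to what the percussion item asks the investigator to judge by hand.

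At stake is the meaning of one descriptive secondary endpoint. Its Improved rate could partly restate the film, and a reader who sets it beside the Day 2 x-ray result would have less independent support than appears. If the order is not recorded at the time, no later analysis can recover it.

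**Working it through.** The plan gives no figure on this point to reproduce, and its sample size is a convenience sample of up to about 15 (Section 3.5.1). The check is a comparison of the text, followed by illustrations on assumed inputs.

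**Text.**
- Rater: the physician investigator (3.4.1), not masked.
- Timing of rating: Day 2, or earlier discharge (3.4.1); after day two of therapy (Appendix 3). No clock time is required in either place.
- Timing of film: Day 2, about 48 hours (3.3). Film date and time are logged (3.1.2, 3.4.1), but that shows when the film was taken, not when the investigator saw it.
- Order of the two: neither stated nor recorded.

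**Illustration 1: films only move ratings upward.** Assume q = 0.40 rated Improved on bedside findings alone, unrelated to the film; p = 0.60 of films improved; and an improved film converts a share u of the remaining ratings to Improved.

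Improved where the film improved = q + (1 − q)u = 0.40 + 0.60u. Where it did not, 0.40. Overall = q + p(1 − q)u = 0.40 + 0.36u.

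| u | Overall | Film improved | Film not improved | Gap |
|---|---|---|---|---|
| 0.1 | 43.6% | 46% | 40% | 6 points |
| 0.3 | 50.8% | 58% | 40% | 18 points |
| 0.5 | 58.0% | 70% | 40% | 30 points |

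In 15 subjects the overall rise is 15 × 0.036 = 0.5 to 15 × 0.18 = 2.7 subjects.

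**Illustration 2: films move ratings both ways.** If a film that has not improved also converts a share u of Improved ratings downward, the rate in that group is 0.40(1 − u). Overall = 0.60(0.40 + 0.60u) + 0.40 × 0.40(1 − u) = 0.40 + 0.20u, which is 42-50% for u = 0.1-0.5. The gap is (0.40 + 0.60u) − 0.40(1 − u) = u, or 10-50 points. In general the overall rate moves by u(p − q), so it need not rise. It does not move at all when p = q, although the gap does.

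**Illustration 3: informal agreement.** Let p = q, from 0.5 to 0.8, with no true association, and let a share f of ratings simply follow the film. Chance agreement is c = pq + (1 − p)(1 − q), expected agreement is f + (1 − f)c, and kappa equals f.

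| f | Expected agreement | Chance that at least 12 of 15 agree |
|---|---|---|
| 0 | 50-68% | 2-24% |
| 0.25 | 62.5-76% | 13-50% |
| 0.5 | 75-84% | 46-79% |

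The documents give no basis for u or f. The illustrations show a direction and a possible scale, not an estimate. They also use one Improved/not-Improved rating per subject, whereas the form scores seven items separately.

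**The case against.** The strongest reply is that nothing the plan intends to compute is damaged. A reader might infer that Section 3.3 relies on this rating to corroborate the film, because it looks for a "corresponding improvement in the clinical respiratory status of the patients", and that contamination would make that correspondence uninterpretable. The documents do not support this. The same sentence goes on to name a lower oxygen requirement and/or better saturation as the evidence and does not name the evaluation. Section 3.5.2 plans no cross-tabulation or agreement measure with the Kelly score. The stronger reading therefore fails, and the gaps and agreement figures above bear only on an informal comparison.

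Other points carry weight:

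- The sample is small. With 60% of 15 films improved, the groups are 9 and 6, and one subject moves a proportion by 1/9 = 11 or 1/6 = 17 points. A 6-point gap is less than one subject.
- The form ties the rating to listed bedside parameters, and Section 3.4.1 expects observations to be documented when they occur. Both limit drift, but neither sets the order or keeps the film from the rater.
- No section says the investigator will see the Day 2 film first. That is so; the point is that nothing prevents it or would reveal it.
- Scoring before the Day 2 film would not make the rating independent of the films. The baseline film qualified the subject, a Day 1 film is also collected, and the treatment is known. This stands and limits what the fix can claim.

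What the reply does not answer is the effect on the evaluation's own result. The Synopsis itself calls this endpoint a "subjective physician assessment", and that is the kind of rating most open to knowledge of the film.

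**Conclusion.** The gap is real and minor. An unblinded, subjective Day 2 rating is made on the same study day as the primary-endpoint film, with no rule on order and no record of it. Film knowledge can shift the rating's Improved rate and makes any informal comparison with the x-ray result harder to interpret, though not worthless.

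The size cannot be derived from the documents. Under the upward-only assumptions above, the Improved rate moves from 40% to 44-58%, about 0.5 to 2.7 subjects in 15. If films move ratings both ways the overall shift is smaller, 42-50%, and it vanishes when the film and bedside rates are equal.

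The primary endpoint is unaffected: the Kelly scores come from masked readers, so contamination runs only from film to bedside rating. The oxygen measures that Section 3.3 names are not touched by this point either.

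**What to change.** In Section 3.4.1 and Appendix 3, require the Day 2 form to be completed from the bedside examination before the investigator views the Day 2 film or its report, where care allows. Add date and time fields and a tick-box for cases in which the film or report was seen first. The tick-box is needed because the logged film time does not show when the investigator saw it. Keep the rating after day two of therapy, as the form already asks, so that the rule does not pull it earlier; apply the same order when the rating is made at an earlier discharge.

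In Section 3.5.2, report the evaluation for all subjects and list which forms were completed before the film.

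The cost is one instruction, the date and time fields, a tick-box and minor scheduling effort. No extra rater is needed and no film is withheld from care. The before-film subset among about 15 subjects may be small, so it should be listed rather than tested. The report should say that open-label expectation and knowledge of the baseline and Day 1 films remain.

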3.5 Statistical Methods and Analysis

3.5.1 Sample Size Estimation:

The sample size for this study is a convenience sample. The study is designed to provide preliminary information on the benefits of the addition of the MetaNeb® System in treating pulmonary atelectasis and associated hypoxemia. Resulting data on the outcomes associated with The MetaNeb® System may help to provide definition of the effect size and variability and the number of subjects required for subsequent studies.

Subjects with a Kelly Score of one (1) or less in both lungs on the baseline (Day 0) chest x-ray will be excluded from the primary endpoint analysis and secondary endpoint analyses related to Kelly Score.

3.5.2 Statistical Analysis:

- Summary statistics and data listings will be provided.
- Demographic data will be summarized. For continuous type data (e. g. Age), descriptive summary statistics (N, mean, median, standard deviation, min, and max) will be presented. For categorical variables (gender, race, etc.) the number and percent of patients in each category will be provided.

Primary Endpoint:

The Kelly atelectasis score at Day 2 will be summarized with shift tables from baseline. Proportion of subjects showing an improvement from baseline will be summarized.

Secondary Endpoints:

- The Kelly atelectasis score at Day 1 and Day 4/discharge will be summarized with shift tables from baseline.
- Time to a Kelly score of 1 in both lungs will be summarized with a Kaplan-Meier curve, with estimate of the median time and a 95% confidence interval.
- To address possible decrease in sample size over time, due to subjects' improvement and stoppage of use of The MetaNeb® System, the Kelly atelectasis score shift from baseline will also be tabulated using LOCF (last observation carried forward).
- Patient reported level of dyspnea (modified Borg dyspnea scale) will be tabulated for each time point.
- The oxygenation index will be summarized by calculating the mean and standard deviation at each time point, as well as for changes from baseline.

Hill-Rom®	Evaluation of The MetaNeb® System to reduce atelectasis as assessed by chest x-ray		
	CBI	06 March 2017	Rev C

- Chest x-ray improvement using a comparative scale after a minimum of forty-eight (48) hours of therapy with The MetaNeb® System
- Oxygenation index (SpO₂/FiO₂ ratio) at Day 1 and Day 4/discharge compared to baseline
- Change in patient respiratory status (Borg Dyspnea Scale – Appendix 2)
- Physician observation and evaluation of patient respiratory status at time of enrollment (baseline) and on Day 2 (Respiratory Status Evaluation – Appendix 3)

Safety:

Incidence of device-related adverse events (adverse device effects) will be tabulated.

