Duration of Subject Participation:	Duration of treatment with The MetaNeb® System will be a minimum of 48 hours, or until the subject is discharged from the hospital (if discharge is earlier). Enrolled subjects will remain in the study through Day 4 or until the subject is discharged from the hospital, whichever occurs sooner.
Number of Subjects:	Up to approximately fifteen (15) subjects will be enrolled.
Study Population:	Post-surgical (thoracic, cardiac or abdominal surgery) non-mechanically ventilated patients with significant atelectasis, as documented by chest x-ray results.
Inclusion Criteria	
Patients who meet all of the following inclusion criteria and no exclusion criteria will be included in the study:
 
 • Post-surgical (thoracic, cardiac or abdominal surgery) • Age \geq 18 years • Significant atelectasis by chest x-ray • Patient meets indication for therapy intervention as defined by Recruitment and Airway Clearance Protocol (Respiratory Department Policy and Procedure) • Signed informed consent

Hill-Rom®	Evaluation of The MetaNeb® System to reduce atelectasis as assessed by chest x-ray	Page 8 of 29		
	CBI	06 March 2017	Rev C	CR-RR2016- 001

Exclusion Criteria:	
Patients who meet one or more of the following exclusion criteria will not be eligible for the study:
 
 • Cause of atelectasis suspected to be infectious or solid mass • Requirement for mechanical ventilation • Requirement for chronic supplemental oxygen • Hemodynamically unstable, as defined by need for vasopressor therapy • Anticipated need for mechanical ventilation or other poor clinical outcome, unrelated to atelectasis or secretion retention • Contraindication to MetaNeb® therapy (untreated tension pneumothorax) • Inability to perform MetaNeb® therapy using a mouthpiece • Anticipated hospital discharge within 24 hours

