3.1 Overview of Study Design

3.1.1 Design:

The study will be a non-randomized open label study. It is a pre-post study design with subjects serving as their own control. All subjects will receive treatment with The MetaNeb® System. The study will be conducted at one (1) site in the US.

The study will evaluate the impact of the therapy on chest x-ray scores and related clinical endpoints. Patients with evidence of significant atelectasis on chest x-ray will be enrolled. After assessing baseline status, therapy with The MetaNeb® System will be introduced and incorporated into the respiratory care treatment regimen. Outcomes will be assessed at regular intervals following the initiation of the therapy.

3.1.2 Procedure:

Up to approximately fifteen (15) patients will be recruited and enrolled from the ICU and/or general care floors. Eligible subjects will be patients who are not intubated, and who have developed clinically significant atelectasis (i.e. described in the radiologist report). Demographic data will be collected from the medical record of each subject at the time of enrollment.

Following enrollment in the study, subjects will receive treatment with The MetaNeb® System per a defined treatment regimen and within the approved product labeling. Treatments will be delivered on a defined schedule. Enrolled subjects will be treated for a minimum of 48 hours, or until discharge (if discharge from the hospital occurs before 48 hours).

Chest x-ray files at baseline (Day 0), for enrolled subjects, will be collected. Daily chest x-ray files for Day 1 (approximately 24 hours), Day 2 (approximately 48 hours) and Day 4 (approximately 96 hours) or discharge (if discharge occurs before Day 4) will be collected as they become available.

All chest x-rays will be logged by subject number, date and time, and event (i.e. Day 0, Day 1 and Day 2, Day 4/discharge) and assigned a number from a random number list. All chest x-rays, identified only by the assigned number will be placed in a file for review and scoring by the blinded radiologist(s).

Pulse Oximetry SpO₂ data along with the subject's oxygen support status (O₂ delivered in LPM or %) from the time corresponding to the baseline and the Day 4/discharge

Hill-Rom®	Evaluation of The MetaNeb® System to reduce atelectasis as assessed by chest x-ray		
	CBI	06 March 2017	Rev C

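### Clearance is seen only at films at about 24, 48 and 96 h or discharge, so the Kaplan-Meier median in 3.5.2 treats an interval as an exact time and can be up to 48 h late

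*Combined protocol and SAP*

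**What the plan says.** Section 3.5.2 (Secondary Endpoints) and the Statistical Methods row of the synopsis both plan the same summary of the time until both lungs score 1 on the Kelly scale: it "will be summarized with a Kaplan-Meier curve, with estimate of the median time and a 95% confidence interval". Neither mentions interval censoring, and neither says which time is assigned to a clearance.

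The scored films are set in 3.4.1: "Chest x-ray files will be collected beginning with the enrollment chest x-ray (Day 0) and for Day 1, Day 2 and Day 4", or discharge if that comes first. Table 1 has the same columns. Section 3.1.2 describes the last film as "Day 4 (approximately 96 hours) or discharge (if discharge occurs before Day 4) will be collected as they become available". Follow-up ends at the same point: "Enrolled subjects will remain in the study through Day 4 or until the subject is discharged from the hospital, whichever occurs sooner" (synopsis, Duration of Subject Participation).

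Each film carries its own time: "All chest x-rays will be logged by subject number, date and time, and event" (3.4.1). Section 3.5.1 calls the sample, up to about 15 subjects, a convenience sample. It removes subjects already at 1 or less in both lungs at baseline from the Kelly analyses. No expected clearance rate or median is given.

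**The concern.** A Kaplan-Meier estimate takes event times as exact. Here a film shows only that clearance happened at some time since the previous film. A logged film time tells us when clearance was seen, not when it occurred. If the event is placed at the first clear film, the dating error has one direction, late. Its largest possible size is the gap between films: about 24 h up to Day 2, then 48 h for a subject who stays to Day 4.

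A reader who sees a median of 96 h would take it as an estimate in hours, when the data say only that it lies after 48 h and by 96 h. The usual confidence interval describes sampling error and leaves out this uncertainty. Section 3.5.1 hopes that the data will help to size later studies. It speaks of effect size and variability and does not name the median time, so a misdated median could be carried forward, but the plan does not say that it will be.

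**Working it through.** The plan has no figure to reproduce. The check asks when the film grid moves the reported median, and how often.

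**Inputs from the documents:** films at about 24, 48 and 96 h (3.1.2, 3.4.1); follow-up to Day 4 or discharge; up to 15 subjects.

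**Assumptions (not in the documents):** the event is dated to the first clear film; all 15 are analysed; every film is present; clearance times are exponential; true median *m* varied from 30 to 120 h. There is no early discharge unless stated.

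**Step 1, one subject.** Clearance just after 48 h in a subject who stays to Day 4 is first seen at about 96 h: 96 − 48 = 48 h late at most. Between daily films the most is 48 − 24 = 24 h.

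**Step 2, the median with 15 subjects.** The reported median is the first film time at which the share not cleared is 0.5 or less, that is, at least 8 of 15 cleared.

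- 3 clear by 24 h and 5 more by 48 h: not cleared at 48 h = 7/15 = 0.467. The median is 48 h, whatever happens later.
- 2 clear by 24 h, 3 more by 48 h, 7 more by 96 h: not cleared at 48 h = 10/15 = 0.667, at 96 h = 3/15 = 0.20. The median is 96 h. If 4 of those 7 had cleared by 72 h, the share not cleared at 72 h was already 6/15 = 0.40, so the true median was at or before 72 h.
- 7 clear in all by 96 h: not cleared = 8/15 = 0.533. No median is reached.

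**Step 3, how often.** The chance of clearance by time *t* is F(t) = 1 − 2^(−t/m). The reported median is at or before *t* with probability P(Bin(15, F(t)) ≥ 8).

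For *m* = 55 h: F(48) = 1 − 2^(−48/55) = 0.454, giving 0.358; F(96) = 1 − 2^(−96/55) = 0.702, giving 0.952. So 96 h is reported with probability 0.952 − 0.358 = 0.594.

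| Assumed true median | F(48) | F(96) | P(reported ≤ 48 h) | P(reported 96 h) | P(not reached) |
|---|---|---|---|---|---|
| 30 h | 0.670 | 0.891 | 0.916 | 0.083 | <0.001 |
| 40 h | 0.565 | 0.811 | 0.696 | 0.301 | 0.003 |
| 55 h | 0.454 | 0.702 | 0.358 | 0.594 | 0.048 |
| 70 h | 0.378 | 0.613 | 0.165 | 0.652 | 0.183 |
| 120 h | 0.242 | 0.426 | 0.014 | 0.264 | 0.722 |

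At a true median of 30 h the most likely reported value is 48 h (probability 0.638), which is 18 h late and comes from the daily grid alone.

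**Step 4, early discharge.** A discharge film shortens the last interval. In 4,000 simulated trials with a true median of 60 h, the reported median was exactly 96 h in 65% of trials with no early discharge. When 40% of subjects left at times spread evenly between 48 and 96 h, it was 96 h in 45% and between 48 and 96 h in a further 20%.

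**Step 5, an added film at 72 h.** Under the Step 3 assumptions it would change the reported median in 42% of trials at a true median of 55 h and in 37% at 70 h.

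**The case against.** The case for leaving the plan alone is fair. This is a descriptive study of about 15 subjects. Time to clearance is not in the endpoint lists of the synopsis or 3.3; it appears only among the analyses. The primary endpoint, the Day 2 score, is untouched. Film times are logged and data listings and shift tables are planned, so a careful reader could rebuild the intervals, and a curve that steps near 24, 48 and 96 h shows its own coarseness. All of that stands, and it makes the point minor. It does not justify printing a single-hour median that the data cannot support.

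Two stronger readings are tempting.

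- A reader might infer that the reported median will be overstated. The documents do not support that. They give no clearance rate and no dating rule, and the 48 h gap matters only if the curve crosses 50% inside it. Sampling error with 15 subjects can also put the median below the truth: at a true median of 55 h, 48 h or less is reported with probability 0.36.
- A reader might infer that the plan ignores Day 3 films that exist, because 3.1.2 calls the films daily. But 3.1.2 names only Day 1, Day 2 and Day 4 or discharge, and says that these files "will be collected as they become available". Nothing shows that Day 3 films are taken. Any that exist may have been ordered because a patient was not improving, and an interval-censored estimate does not repair inspection times that depend on the outcome.

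**Conclusion.** The point holds as a limit of the stated method. Event times are interval-censored, and the plan summarises them as if they were exact. The late dating is at most 48 h when the median falls between 48 and 96 h and at most about 24 h when half clear by 48 h; no median exists if fewer than half clear by 96 h. Which case applies cannot be known beforehand. The size rests on first-clear-film dating, which is inferred, and the probabilities rest on the assumed exponential times, complete films and 15 analysed subjects. Early discharge reduces the effect but does not remove it. This is a low-priority improvement to the analysis, not a flaw in the primary result.

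**What to change.** Change the time-to-clearance sentence in 3.5.2 and in the synopsis in one of two ways.

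1. Use an interval-censored (Turnbull) estimate. Each subject contributes the interval from the last film not cleared to the first film cleared, from the logged film times; a subject never seen clear is censored at the last film. Report the median as an interval, such as after 48 h and by 96 h.
2. Or report the cumulative proportion cleared at each scored film (Day 1, Day 2, Day 4/discharge) with a 95% confidence interval, and state the denominator and the handling of missing films. This matches the proportions already planned in the synopsis and is the simpler choice at this sample size.

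If a Kaplan-Meier curve is kept for display, state the dating rule and label its steps as film times. Note as a limitation that discharge films may be timed by recovery, which the interval method assumes is not the case.

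The cost is a few lines of analysis wording, slightly more programming, and a time figure that looks less precise. No film, read or visit is added. Scoring Day 3 films that happen to exist is optional and should be a sensitivity analysis at most.
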